**Tracing:**

NDI: The measurements at the beginning of the study (baseline measures), 3 days after the last intervention and after 1 month post-study.

Quality of life (SF-36): The measurements in this case will be taken at the beginning of the study (baseline measures) and after 1 month post-study.

## f. Participants Schedule

### **g. Sample**

The sample size has been calculated following the following parameters:

Randomized clinical trial, with 3 branches of study, a minimum detectable change in the NDI of 5 points (10%), 80% statistical power and a standard deviation of 7.

Accepting an alpha risk of 0.05 and a beta risk of less than 0.2 in a bilateral contrast will require 46 subjects in each group, that is, an  $n = 132$ .

The value of estimated losses is 10% of the total.

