### **c. Interventions**

The test will be carried out with 3 branches (2 experimental + 1 control).

- All groups (1, 2 and 3) will conduct a home-based pattern of combined exercises based on stretching, active anti-resisted exercises and joint mobility exercises focused on the cervico-dorsal and scapulo-thoracic regions. Whose clinical effectiveness has shown significant positive changes in pain levels and cervical functionality.
- The two experimental groups (group 1 and group 2) will also receive Osteopathic Manipulative Treatment (OMT) whose description is detailed below: (description based on the TIDier intervention report guide).

The TMO is a 100% manual intervention that is applied individually with a direct contact between therapist and patient.

- Groups 1 and 2 will receive 3 sessions of BMT.
  - Group 1 will receive 3 sessions with a weekly frequency (with + -2 days of margin: between 5 and 9 days).
  - Group 2 will receive 3 sessions at the rate of one session every 3 weeks (with + -2 days of margin: between 19-23 days).

The clinical experience of the therapists participating in the intervention indicates that 3 sessions could be a sufficient number to achieve changes in the clinic of patients with nonspecific cervical pain and that these may be clinically significant, either immediately after the intervention and in the middle term (1 month post-intervention).

From the same clinical experience it is considered that an interval of between 1 and 3 weeks is the most common during the course of a treatment to a patient with nonspecific neck pain.

Therefore, it is considered necessary to compare whether there may be differences applying a greater or lesser frequency within the most usual range of applied treatment.

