### **h. Randomization**

A pragmatic experimental comparative trial with three branches of study (osteopathic treatment with 2 different dosages versus active muscle exercise) is proposed.

After obtaining informed consent (see **Appendix 1**. Information sheet and Informed Consent), patients who meet the inclusion criteria will be awarded to the study groups following a random sequence generated by computer and stratified by each centre. The assignment through the opaque envelope system will guarantee the concealment of said assignment.

The generation of the sequence and the preparation of the opaque envelopes will be done by an external researcher not involved in the interventions.

The recruitment of the participants, and their assignment to the study groups will be carried out by the same people in charge of carrying out the intervention..

|

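### The sample size contradicts itself: 46 in each of three groups is 138, not 132, and the place of the 10% losses is not stated

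*Protocol*

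**What the plan says.** The Protocol's Sample section sizes a three-arm trial on "a minimum detectable change in the NDI of 5 points (10%), 80% statistical power and a standard deviation of 7". The error rates are set by "Accepting an alpha risk of 0.05 and a beta risk of less than 0.2". The result of the calculation is then worded "in a bilateral contrast will require 46 subjects in each group, that is, an", and the total printed at that point is 132. The two figures are offered as equivalents. A separate sentence follows: "The value of estimated losses is 10% of the total".

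The number of arms is not in doubt. The Interventions section describes two experimental groups and one control, and the Randomization section calls the study "A pragmatic experimental comparative trial with three branches of study". No section of the protocol at hand describes unequal allocation or gives another total.

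**The concern.** Three groups of 46 are 138 patients, and 132 patients are three groups of 44, so one of the two printed figures must be wrong. The sentence on losses adds a second uncertainty, because it does not say whether the 10% lies inside the printed number or still has to be added.

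The sample size is the recruitment target. A trial that stops at 132 meets the printed total and leaves each arm 2 short of the printed 46. Whether recruitment was completed as planned would then depend on which figure the reader takes.

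**Working it through.** **Inputs, all from the Sample section:** difference 5 NDI points, SD 7, two-sided alpha 0.05, power 80%, three arms, 46 per group, total 132, losses 10%.

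**1. The printed total**
- 46 × 3 = 138, so 132 is not reproduced.
- 132 / 3 = 44.
- 138 − 132 = 6, and 6 / 132 = 4.5%.

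**2. Do the losses bridge the gap?**
- 138 × 0.9 = 124.2.
- 132 / 0.9 = 146.7.
- 132 / 138 = 0.957, not 0.90.

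They do not.

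**3. Do the printed inputs identify the right figure?** For a plain two-group comparison:

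n per arm = 2 × (1.960 + 0.842)² × 7² / 5² = 30.77, so 31. The exact t-test needs 31.76, so 32 (power 0.803). Divided by 0.9 these become 34.2 and 35.3, so 35 to 36 per arm. That is neither 44 nor 46.

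Each printed figure can be reached, but by a different method that the protocol does not state:
- *44 per arm:* a three-arm F-test with means at −2.5, 0 and 2.5 has effect size f = √(12.5 / 3) / 7 = 0.292 and needs 38.8, so 39 per arm. 39 / 0.9 = 43.3, so 44 per arm and 132 in total.
- *46 per arm:* Bonferroni for three pairwise comparisons, normal approximation, gives 2 × (2.394 + 0.842)² × 49 / 25 = 41.04. 41.04 / 0.9 = 45.6, so 46 per arm and 138 in total.

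No single method tried gives both. Both routes count the losses as already included.

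**4. Consequence for power if losses are included.** Evaluable patients per arm are 44 × 0.9 = 39.6 or 46 × 0.9 = 41.4. For a difference of 5, SD 7 and two-sided alpha 0.05:

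| Per arm | Evaluable | Power, pairwise t | Power, F (evenly spaced means) | Detectable at 80%, t | Detectable at 80%, F (evenly spaced) |
|---|---|---|---|---|---|
| 44 | 39.6 | 0.881 | 0.809 | 4.46 | 4.95 |
| 46 | 41.4 | 0.895 | 0.827 | 4.36 | 4.84 |

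Evenly spaced means are an assumption, since the protocol gives no pattern. With two arms equal and the third 5 points away, the F-test power is 0.911 and 0.923.

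**5. If losses come on top.** The number to randomise is 132 / 0.9 = 146.7, so 147, or 138 / 0.9 = 153.3, so 154. The possible readings therefore run from 132 to 154.

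**The case against.** The strongest reply is that the practical weight is small: two patients per arm, one sentence to correct, and neither figure takes power below 80% at the printed alpha. That stands, and the point should be read as a contradiction to settle, not as an underpowered trial.

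Three further objections deserve an answer.

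- **Both figures have a plausible origin.** This is true, as step 3 of the working shows. But the two origins are different calculations and neither is stated, so a reader still cannot tell which figure to keep. That both work only with losses included suggests this is what was meant; it does not establish it.
- **The reassurance on power depends on an unadjusted alpha.** This is also true. With Bonferroni for three comparisons, which the protocol does not state, t-test power after 10% losses is 0.77 for 44 per arm and 0.79 for 46, and the detectable differences are 5.19 and 5.07 points, slightly above 5. How multiplicity is handled may properly sit in a statistical analysis plan that is not at hand, so no fault is found there.
- **Parts of the document are missing.** Some pages were removed and a figure is not shown. Nothing indicates that they settle the point, and they would not change the fact that the Sample section contradicts itself in one sentence.

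**Conclusion.** The sample size is wrong as written. For three equal arms, 46 per group and a total of 132 cannot both hold; they differ by 6 patients, and losses do not account for the difference. The protocol does not show which figure is the slip. Whether losses are included is a secondary ambiguity, but it widens the range of possible targets more than the arithmetic slip does (22 patients against 6).

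At the printed alpha the power consequence is slight: one percentage point by t-test and two by F-test between the two figures, with all four values above 80% after 10% losses. This rests on the stated SD of 7, equal allocation, an unadjusted two-sided 0.05 and, for the F-test, evenly spaced means. The contradiction itself needs only equal allocation across three arms.

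**What to change.** Restate the Sample section so that it gives:

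- one per-group number with its matching total: either 44 per group and 132, or 46 per group and 138;
- whether the 10% losses are inside that number; if they come on top, the number to randomise as a separate figure;
- the test used for sizing, and whether the printed 0.05 was applied as it stands or divided among comparisons. The sponsor has to supply this from the calculation actually run, because it decides which figure is right;
- preferably, the power of the evaluable number under that test.

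The cost is one corrected sentence. If losses are already included, keeping 132 needs no extra patients and keeping 46 per group needs 6. If losses come on top, the number to randomise rises to about 147 or 154, which is 15 or 22 more than 132.

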### **h. Randomization**

A pragmatic experimental comparative trial with three branches of study (osteopathic treatment with 2 different dosages versus active muscle exercise) is proposed.

After obtaining informed consent (see **Appendix 1**. Information sheet and Informed Consent), patients who meet the inclusion criteria will be awarded to the study groups following a random sequence generated by computer and stratified by each centre. The assignment through the opaque envelope system will guarantee the concealment of said assignment.

The generation of the sequence and the preparation of the opaque envelopes will be done by an external researcher not involved in the interventions.

The recruitment of the participants, and their assignment to the study groups will be carried out by the same people in charge of carrying out the intervention..

|

### **i. Masking**

A double masking is proposed.

Three active interventions are compared.

The patients will be blinded in relation to the study group they belong to, ensuring the masking of the participants.

The data that is intended to be obtained for its analysis are of a self-reported nature and will be collected and administered by an external investigator not linked to the interventions, ensuring the masking of the evaluator.

Due to the nature of the interventions, masking of therapists is not possible.

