## **c. Trial Design**

Randomized, pragmatic, double-blind controlled clinical trial.

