#### **d. Procedures**

At the beginning of the 1st session, a battery of questions will be made as an anamnesis with the objective of evidencing possible risk factors at the therapeutic level (see **Appendix 4**. Patient data collection form). The presence of one or more risk factors will suppose the exclusion of the patient from the study.

Next, a brief osteopathic musculoskeletal evaluation will be made to the patient. This exploration will follow a standardized protocol for all patients in the experimental groups (1 and 2).

The tests to be carried out will be:

- Observation (standing patient):
  - Assessment of the anterior projection of the head
  - Assessment of the variation in the physiological curves of the spine
- Active test of the cervical spine with the patient in a sitting position.
  - Flexo-Extension / Rotations / Lateral inclinations
- Segmental test of joint mobility of the cervical and dorsal spine (patient in sitting and supine position)
- Passive mobility test of the cervical spine (patient in the supine position):
  - Flexo-Extension / Rotations / Lateral inclinations

The combination of exercises scheduled at home for all groups is based on the conclusions of different studies, and will consist of:

- Self-resisted active exercise in flexion, rotations and inclinations of the cervical spine.
- Active mobility in its maximum travel (without forcing pain) in flexion, rotations and inclinations of the cervical spine.
- Stretching upper trapezius muscles and scalenes.
- Active mobility in circumferential joints of the glenohoumeral joint, and in flexo-extension of the thoracic spine.

Said guideline will be shown to the patient during the first visit, and will be accompanied by a visual support with the detail so that he remembers it and can do it at his home.

The work schedule will be carried out for 7 weeks, at a rate of 5 sessions per week.

It will be the patient himself who will keep a diary record of the activity carried out during the weeks that the trial lasts. The diary will be facilitated by the therapists, and in it the exercises to be performed will be indicated.

For groups 1 and 2, a total of 3 techniques selected from a list of 7 available techniques common to all centers will be applied in each session. The choice of techniques will be based on the results of the examination performed, the particularities of the patient and the clinical experience of the osteopath. In each

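### The trial is called double-blind with masking ensured, but in OMT versus exercise alone the patient knows whether manual treatment was given and is also the outcome rater

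*Protocol*

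**What the plan says.** Section 2.c describes the study as "Randomized, pragmatic, double-blind controlled clinical trial". Section 3.i repeats the label ("A double masking is proposed") and makes two specific claims:

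- **Patients:** "The patients will be blinded in relation to the study group they belong to, ensuring the masking of the participants".
- **Evaluator:** the self-reported data "will be collected and administered by an external investigator not linked to the interventions, ensuring the masking of the evaluator".

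The only exception conceded is the therapists, who cannot be masked. Neither section limits its claim to a particular comparison.

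The main goal (section 2.b) is OMT versus an exercise plan. Under section 3.c all three groups do the home exercises, and only groups 1 and 2 also have three sessions of OMT. That treatment is described thus: "The TMO is a 100% manual intervention that is applied individually with a direct contact between therapist and patient". In section 3.d the standardised osteopathic examination is set out for groups 1 and 2 only. The exercise programme reaches every patient in the same way ("Said guideline will be shown to the patient during the first visit") and is then done at home. According to section 3.e the patient completes the questionnaires and hands them in at the centre that gave the treatment.

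**The concern.** Double-blind tells a reader that neither the participant's nor the assessor's knowledge of treatment can have moved the outcome. Here the primary comparison is between patients who were treated by hand three times and patients who were not, and both outcomes are the patient's own ratings. If the label stands, a difference in NDI or SF-36 between OMT and exercise alone could be reported as a double-blind result although it may include expectation and therapist-contact effects. The protocol would be claiming a protection against bias that its main comparison does not have.

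**Working it through.** **1. Masking claims against the design, by comparison**

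| Question | OMT (group 1 or 2) vs exercise alone (group 3) | Group 1 vs group 2 |
|---|---|---|
| Hands-on treatment | Groups 1 and 2 only (3.c) | Both |
| Osteopathic examination | Described for groups 1 and 2 only (3.d) | Both |
| Sham or attention contact in the comparator | None described (3.c, 3.d) | Not needed |
| Can the patient be unaware of the difference? | No: manual treatment is either felt or absent | Possibly, if the other schedule is not disclosed |
| Who rates NDI and SF-36? | The patient (3.e, 3.i) | The patient |

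For the main comparison the patient therefore knows whether manual treatment was given. Because the patient supplies the score, the evaluator is unmasked as well. An investigator who only handles the forms does not rate anything, so that investigator's independence cannot mask the rating. This does not imply that the investigator knows the allocation.

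**2. What a reporting shift could do (illustration only)**

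The protocol has no figure for reporting bias, so there is none to reproduce.

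- From section 3.g: SD 7, two-sided alpha 0.05, 46 per group, a total of 132, 10% losses.
- Group sizes used: 46; 132/3 = 44; 46 × 0.9 = 41.4, taken as 41.
- Assumed: true effect 0; a shift b of 1, 2 or 3 NDI points in favour of OMT; two-sample t-test. A second alpha of 0.05/3 = 0.0167 is also assumed, in case three pairwise comparisons are adjusted.

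Formulas: SE = 7 × √(2/n); df = 2n − 2; the probability of significance is the two-sided rejection probability of a noncentral t with noncentrality b/SE; the smallest significant observed difference is t(1 − alpha/2, df) × SE.

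Example, n = 46: SE = 7 × √(2/46) = 1.460. For b = 2 the noncentrality is 2/1.460 = 1.370. The critical t on 90 df is 1.987, so the rejection probability is 0.273. The smallest significant difference is 1.987 × 1.460 = 2.90 points.

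| Alpha | n per group | b = 1 | b = 2 | b = 3 | Smallest significant difference (points) |
|---|---|---|---|---|---|
| 0.05 | 41 | 0.098 | 0.248 | 0.483 | 3.08 |
| 0.05 | 44 | 0.102 | 0.263 | 0.511 | 2.97 |
| 0.05 | 46 | 0.104 | 0.273 | 0.529 | 2.90 |
| 0.05/3 | 41 | 0.041 | 0.131 | 0.313 | 3.78 |
| 0.05/3 | 44 | 0.043 | 0.141 | 0.338 | 3.64 |
| 0.05/3 | 46 | 0.044 | 0.148 | 0.355 | 3.56 |

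With no shift these rates would be 5% and 1.7%. In every row a difference below the protocol's 5-point relevant change would already be significant. That is ordinary for a trial powered for 5 points and is not itself a fault; it shows only that a shift need not be large to matter.

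**The case against.** The strongest reply is that section 3.i may mean masking to arm status or hypothesis: all three interventions are active, and a patient who is not told of the other arms need not know which group is the control. The information sheet (Appendix 1) is not available, so this cannot be ruled out, and such non-disclosure could reduce differences in expectation. It cannot, however, hide whether hands-on treatment was given, nor equalise therapist contact. The participant schedule (3.f) is also not readable here, but a sham would be expected in section 3.c, and none is there.

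Second, a pragmatic trial need not be masked, and therapist contact is arguably part of the treatment delivered. That is fair, and it is why no sham or change of design is asked for. It does not justify the double-blind label, and it does not cover expectation-driven reporting.

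Third, an external administrator of the questionnaires is a real, if limited, safeguard against prompting or mishandling. That stands, but it is not masking of a self-rated score. Delivery to the centre can also be squared with external collection if the investigator collects the forms there. The protocol leaves the route unclear rather than contradictory.

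Finally, the shifts are assumed, run in one direction, and are not lowered by rewording. All true; the finding does not rest on them.

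**Conclusion.** The concern holds. For OMT versus exercise alone, the statements that the trial is double-blind and that participant and evaluator masking is ensured are wrong as written. This follows from the protocol's own description of the arms and outcomes and needs no numerical assumption. It is a design statement made in the protocol, so a statistical analysis plan could not put it right.

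The size of any bias is unknown. Under assumed shifts of 1, 2 or 3 NDI points, the chance of a significant difference with no true effect is about 10%, 25-27% or 48-53% at two-sided 0.05, and about 4%, 13-15% or 31-36% at 0.05/3.

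The finding does not extend to group 1 versus group 2, where patients may be unaware of the alternative schedule. It should be corrected, but the trial remains feasible and interpretable once it is described accurately.

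**What to change.** - **Section 2.c:** drop the unqualified double-blind label and refer to section 3.i for masking by comparison.
- **Section 3.i, patients:** replace the double-masking sentence and the sentence on patients with: *For OMT versus exercise alone, patients and therapists are not masked and the outcomes are self-rated by unmasked patients, so a difference in NDI or SF-36 may include expectation and therapist-contact effects.* Limit any claim of participant masking to group 1 versus group 2 (unaware of the alternative schedule), and make it only if the information sheet supports it.
- **Section 3.i, evaluator:** replace the claim of evaluator masking with a statement that the external investigator only collects and administers the questionnaires. If that person is to be kept unaware of allocation, say so separately, without presenting it as masking of the rating.
- **Section 3.e:** have questionnaires returned directly to that external investigator instead of to the treating centre, so that the route agrees with section 3.i.

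The cost is wording in three sections, return envelopes or e-mail return, and a less favourable design label. Design, sample size and analysis do not change.

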#### **4. Ethics**

---

This protocol will be presented at the Escola d'Osteopatia de Barcelona, as part of the development of a research project to obtain the D.O. (diploma in osteopathy). Prior to the development of the trial, it will be presented to the Clinical Ethics Committee of Bellvitge Hospital for approval.

The recruitment of participants will be done under the signature of the informed consent (see **Appendix 1**).

The centres where the study will be carried out are of a private nature, and the development of the trial will not entail any cost for the patient in the interventions received.

The people in charge of informing the study, obtaining the signature of the informed consents and carrying out the interventions will be the OH, ES and DP researchers.

The patient may leave the study at any time, without prior notice and without specifying the reason.

Participation in this clinical trial by patients does not imply any increase in risk in relation to usual clinical practice. Comparative interventions are common in osteopathic manual practice.

Randomization, preparation of opaque envelopes and data monitoring will be carried out by GA.

The clinical and personal data of the participants will be coded numerically, and

|

this relationship is kept in the custody of the research team. Likewise, the processing of these data will be in accordance with the provisions of the LOPD 15/1999 and the General Data Protection Regulation (EU) 2016/679. In no case will this information be disclosed to people outside the study.

This clinical study will be carried out in accordance with the principles of the Declaration of Helsinki (Fortaleza, 2013).

Declaration of conflicts of interest: No.

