## **e. Variables**

### Main Variable:

- o Neck Disability Index (NDI).

This index is the most used in cervical pain assessments. It is a test of 10 questions with 6 possible answers, which punctuate aspects such as the intensity of cervical pain or the degree of limitation in the main activities of daily life.

The score covers the range of 0 to 50 points, the degree of involvement in cervical functionality being greater the higher the score obtained in the test.

We establish the minimum change to be detected (minimum clinically relevant change) at 5 points. The Spanish version of the NDI will be used, validated by Andrade Ortega,JA et al.

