### Secondary Variable:

- o Degree of general quality of life, through the SF-36 health questionnaire.

The data will be reported in the form of a report by the patient himself, who will receive via e-mail (whenever possible) or in printed form the questionnaire to be completed and will deliver to the same centre in which the intervention has been carried out.

Adverse effects: A record of any adverse effects that may be occur during the study, these being detailed in the same patient control sheet (see **Appendix 4**).

[figure not shown]

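### Questionnaires go back to the treating centre while evaluator masking rests on external collection, so independent handling of the outcomes is not secured as written

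*Protocol*

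**What the plan says.** Only the protocol is at hand. Five places bear on who handles the outcome forms.

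- **Section 3.i, Masking.** The self-reported data "will be collected and administered by an external investigator not linked to the interventions, ensuring the masking of the evaluator". This is the only ground offered for evaluator masking. The same section concedes: "Due to the nature of the interventions, masking of therapists is not possible".
- **Section 3.e, Variables.** Under the secondary variable, after the SF-36 entry, the patient is the one "who will receive via e-mail (whenever possible) or in printed form the questionnaire to be completed" and who then "will deliver to the same centre in which the intervention has been carried out". The NDI, the main variable, is described just before ("It is a test of 10 questions with 6 possible answers") with no return route of its own.
- **Section 3.h, Randomization.** Sequence and envelopes are made outside the treating team: this "will be done by an external researcher not involved in the interventions". Recruitment is not: the participants' recruitment and "their assignment to the study groups will be carried out by the same people in charge of carrying out the intervention".
- **Section 4, Ethics.** "Randomization, preparation of opaque envelopes and data monitoring will be carried out by" one person. Participant data are to be coded by number, and the key stays with the research team; no role is named for it.
- **Appendices 2 to 4.** The NDI form asks for name, age, address and profession. The SF-36 form carries a participant ID. The patient data sheet has fields for the patient's name and the assigned group side by side.

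**The concern.** Section 3.i claims a property (the evaluator is masked) on one ground (an outsider collects the data). Section 3.e sets a route that brings the completed questionnaire back to the clinic where unmasked therapists recruit, assign and treat. If the form passes through that clinic, the ground for the claim is weakened.

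The patient rates both outcomes, so the issue is not an assessor's scoring. It is the setting in which patients answer and who sees or follows up their forms. Two effects are plausible:

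- **Courtesy answering.** A patient who hands a named form to the clinic that treated them may answer more kindly than one who returns it elsewhere.
- **Arm-dependent chasing.** Staff who know the arm and see which forms are missing can remind patients unevenly, so that missing data depend on arm.

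Both could differ by arm, because section 3.c gives groups 1 and 2 three hands-on sessions each and group 3 none. The comparison most exposed is the main one, osteopathic treatment against exercise. The comparison of session frequencies is less exposed, since both of its arms have the same number of sessions.

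**Working it through.** The point rests on no sample size, power or alpha formula, and the protocol gives no figure to reproduce. The check sets the sections side by side and then bounds the number of forms.

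**1. Do the two routes agree?**

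| Question | Section 3.e | Section 3.i |
|---|---|---|
| Who or what receives the completed form? | The centre that treated the patient | An outside investigator |
| Recipient at the centre named? | No | Not applicable |
| Sealed or coded return? | Not mentioned | Not mentioned |
| Staff at that place masked? | No (sections 3.h and 3.i) | Presented as masked |

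They do not agree as written, and nothing in the protocol reconciles them.

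**2. Does the return sentence reach the NDI?** Its position, after the SF-36 entry and with a single questionnaire in view, points to the SF-36. Its subject, the data in general, and the absence of any other NDI route point to both. The NDI is also filled in by the patient (Appendix 2). Coverage of the NDI is a reasonable reading, not a stated fact. If it is wrong, the conflict remains for the SF-36, because section 3.i covers all self-reported data, and the primary outcome then has no stated return route.

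**3. Could a returned form be matched to an arm?** Yes, if it is a paper NDI form. Appendix 2 puts the name on it, and Appendix 4 puts name and assigned group on one sheet. This sits badly with the numerical coding promised in section 4.

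**4. How many forms at most?** Inputs: NDI at baseline, 3 days after the last intervention and 1 month after the study; SF-36 at baseline and 1 month (section 3.e, follow-up part); 46 per group in 3 groups, or a total of 132 (section 3.g). The two sample-size figures differ (46 × 3 = 138), which is a separate matter, so both are carried. Eligibility needs an NDI score, so the baseline NDI precedes allocation; only later forms count.

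- Post-baseline NDI forms: 2 × 132 = 264; 2 × 138 = 276.
- Post-baseline SF-36 forms: 1 × 132 = 132; 1 × 138 = 138.
- Patients expected lost at 10%: 0.10 × 132 = 13.2; 0.10 × 138 = 13.8, so about 13 to 14.

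The form counts are upper bounds. Losses reduce them, and so would replies by e-mail, whose share is not given.

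**5. What could it do to the estimate?** The documents give no size. If courtesy answering shifts the osteopathic arms by d NDI points against exercise, the shift is d/5 of the 5-point minimum relevant change. For an assumed d between 0 and 1 this is 0/5 = 0% to 1/5 = 20%. This is an illustration of scale, not an estimate.

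**6. What does the shared role in section 4 add?** One person randomises, prepares envelopes and monitors data. The protocol does not say that this person keeps the list, scores outcomes or is the investigator of section 3.i, and it does not define data monitoring. So the separation of allocation from outcome data is not secured, but section 3.i is not contradicted.

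**The case against.** The strongest case is that the two routes can coexist: patients leave forms at the site, and the outside investigator picks them up. Delivery to a centre is not handling by a therapist, e-mail is the preferred way of sending, and the delivery clause may concern printed forms only. That is possible, and it is why the form counts are only upper bounds. But the protocol does not say so, and a masking claim that depends on an unstated arrangement is not secured.

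Four stronger readings are tempting, and the documents do not support them:

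- *Primary-outcome forms are certainly returned to the therapists.* The sentence stands under the secondary variable, does not name the NDI, and names no recipient.
- *The person who monitors the data holds the randomisation list, so the evaluator is unmasked.* Custody of the list is not stated. The custody sentence in section 4 concerns the numerical coding. The sequence generator is described as external to the interventions, and a monitor who knew the allocation could not change a patient's own answers.
- *The bias favours osteopathic treatment.* Courtesy answering would plausibly do so, but the direction of uneven chasing depends on which patients are chased and how they fare.
- *Masking is shown to have failed.* The text shows only that it is not secured.

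Two further objections stand in part. Courtesy towards the therapist may persist whatever the return address, so the fix reduces the effect and may not remove it. And the time at which allocation is linked to the data is often left to a statistical analysis or data management plan, so that part is offered as a safeguard and not as an omission.

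**Conclusion.** The point holds in a limited form. The return route in section 3.e conflicts with the external collection in section 3.i, and the staff at the place of return are unmasked. Evaluator masking and independent handling of the self-reported outcomes are therefore not secured as written.

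Reach: at most 264 to 276 post-baseline NDI forms, on the reasonable reading that the sentence covers the NDI; otherwise at most 132 to 138 post-baseline SF-36 forms, with the NDI route left unstated. About 13 to 14 expected losses are where uneven reminders could act. The effect on the estimate is unknown in size and unproved in direction; the 0 to 20% of the target difference shown above rests wholly on an assumed shift of 0 to 1 point.

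The shared role in section 4 is a secondary weakness. The change should be made, because it is cheap and protects the primary comparison.

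**What to change.** 1. **Section 3.e:** state that all follow-up NDI and SF-36 forms go directly to the outside investigator already named in section 3.i, by e-mail or, for paper, in a sealed pre-addressed envelope. State explicitly that this covers the NDI.
2. **Reminders:** have them sent by that investigator, on the same schedule in all three arms.
3. **Appendix 2:** replace name and address on the NDI form with the participant code, as the SF-36 form already does with its participant ID.
4. **Section 4, as a secondary safeguard:** keep the allocation list apart from the outcome file and do not link them until the NDI scores are entered and locked. Say whether the person who randomises is also the investigator of section 3.i; if so, someone else should keep the list until then.

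Cost: postage for paper forms and minor administration. Item 4 may need another custodian for the list if the two roles are held by one person, which the protocol does not settle. No visit, measurement or treatment changes.
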